Methods: Up to 40 participants will be enrolled in order to accrue 32 participants who complete the study protocol. As shown in **Figure 3**, all study participants will undergo a biospecimen collection at baseline and day 28 including blood, saliva, and pancreatic juice (PJ). PJ will be collected during endoscopic pancreatic function tests (ePFT). Up to 4 weeks may elapse between the baseline biospecimen collection and day 1 of study drug administration. 16 participants will receive oral indomethacin 50 mg BID, and 16 will receive matched placebo BID. Participants will complete the Brief Pain Inventory (BPI) and PROMIS 10 quality of life instrument at baseline and day 28, and will also complete daily symptom and medication diaries.

Definitions: CP will be diagnosed per American Pancreatic Association criteria for definite CP. These include a compatible clinical picture with definite findings of CP (Cambridge 3-4 ductal changes, and/or calcifications) on cross-sectional imaging studies.

Study Interventions and Measures: The *endoscopic pancreatic function test (ePFT)* will be performed at baseline and on day 28. ePFT is a standardized test used in medical pancreatology clinical practice that involves administration of intravenous secretin (0.2 mcg/kg slowly over one minute) to stimulate pancreatic juice secretion, followed by aspiration of pancreatic juice from the duodenum via an endoscope. Some subjects will undergo a baseline ePFT as part of their routine clinical care; other subjects, who are having upper GI endoscopy or endoscopic ultrasound (EUS) performed as part of their clinical care, will undergo ePFT during endoscopy for research purposes. Fluid will be aspirated from the duodenum via an endoscope at baseline and from 0-10 and 10-20 minutes following secretin administration, and processed per CPDPC pancreas juice/fluid SOP. Participants will be instructed to take their study drug 2 hours prior to their follow-up research endoscopy with ePFT on day 28.

PJ bicarbonate and lipase concentrations will be measured on duodenal aspirates from each time point using a previously validated method. ¹⁸ *PGE₂ concentrations* will be measured in saliva, blood, and pancreatic juice from baseline and day 28 using a tandem mass spectroscopy assay developed and validated at Mayo Clinic Rochester. *Peak IN drug levels* will be measured in blood on day 28, providing an assessment of participant compliance with study drug administration.

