The *Brief Pain Inventory (BPI)* and the *PROMIS-10* are validated scales that quantify pain and quality of life, respectively, and will be completed at baseline and day 28. A *medication and pain diary* will be completed daily by all subjects at baseline and during the 28-day treatment period,

including all narcotics and over-the-counter medications used. Oral opioid usage will be expressed in oral morphine equivalents for purposes of data analysis.

Randomization, Allocation and Blinding

Randomization: Subjects will be assigned to receive IN or placebo according to a computer generated randomization list composed of randomized blocks of sizes of 2 or 4. Two separate sets of blocks will be created, one for subjects with alcoholic CP and the other for those with other causes of CP. Within each block, equal number of subjects will be assigned to IN and placebo. Separate sets of randomization blocks will be provided for Mayo and Ohio State. The randomization lists will be computer generated by the study statistician ([name]), and kept in a secure computer file and paper study binder in the Mayo and Ohio State Research Pharmacies. No investigators or study personnel other than [name] will have knowledge of the randomization list. [name] will not participate in any aspect of subject recruitment, subject allocation, conduct of the study, or data ascertainment, but will perform data analysis.

Subject allocation will be known only to the staff of the Mayo and Ohio State Research Pharmacies, who will assign subjects to IN or placebo according to their randomization list provided by [name]. Allocation will be performed by matching the subject's study number with the randomization list. Allocation will not be revealed to subjects, investigators, other study personnel, or clinicians caring for subjects until all subjects have completed the clinical trial or for medical emergency. Because subjects, investigators, and study personnel will be blinded, they will not be able to determine subject allocation before or during data ascertainment.

In case a subject is allocated to receive study medication, but is withdrawn from the study before completing the protocol, study medication will be returned to the Research Pharmacy for disposal, and the following subject will be assigned the same allocation. All investigators will remain blinded to the allocation of the withdrawn subjects and their replacements.

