5.2 EXCLUSION CRITERIA

1. Diagnosed with acute pancreatitis requiring hospitalization within the 6 weeks prior to study enrollment.
2. Habitual use of aspirin or non-steroidal anti-inflammatory medications (NSAIDs), defined as use more than once per week.
3. Any use of aspirin or NSAIDs within 1 week of baseline study endoscopy procedure.
4. Allergy to secretin, indomethacin or NSAIDs.
5. History of known chronic renal insufficiency or cirrhosis.
6. History of coronary artery disease, angina pectoris, myocardial infarction, cerebrovascular accident (stroke), or transient ischemic accident (TIA).
7. History of peptic ulcer or gastrointestinal bleeding.
8. Incarcerated.
9. Found to have active GI ulceration at the time of baseline endoscopy.
10. Hospitalized for acute pancreatitis while participating in this research protocol.
Participants who are hospitalized for an episode of acute pancreatitis during study participation will be withdrawn from the study, and considered non-accrued.
11. Patients with indwelling pancreatic duct stents.
12. Patients status post Whipple procedures or Roux-en-Y gastric bypass due to inability to collect pancreatic fluid via the natural ampulla, unless having an EDGE procedure for clinical reasons.

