7.2 PARTICIPANT DISCONTINUATION/WITHDRAWAL FROM THE STUDY

Participants are free to withdraw from participation at any time upon request. An investigator may withdraw a participant from the study for the following reasons:

1. Found to have active gastrointestinal ulceration at the time of their baseline, clinically indicated GI endoscopy procedure.
2. Positive pregnancy test in a woman of child bearing potential.
3. Significant study medication non-compliance (defined as failure to take at least 66% of study medication doses, as determined during telephone follow-up calls).
4. Hospitalized for acute pancreatitis during study participation.
5. Other acute illness that requires breaking study blinding and discontinuing study medication for clinical reasons.

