9.3 POPULATIONS FOR ANALYSES

Given the small sample size of this pilot study, the entire study population completing the study protocol will be utilized for most analyses. Per-Protocol analysis will be used primarily (e.g., participants who took at least 80% of study intervention for 80% of the days within the treatment period).

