9.4.2 ANALYSIS OF THE PRIMARY EFFICACY ENDPOINT(S)

For the Primary Endpoint/Specific Aim 1, the primary analysis will be a linear random intercept model that incorporates PJ PGE₂ data from both baseline and day 28 from all randomized patients. Transformation will be used as appropriate to reduce the skewness of data and satisfy modeling assumption. The model includes randomized groups, time, and their interactions as fixed effect covariates, from which the mean change in PJ PGE₂ will be estimated for each randomized group. Effects of additional covariates, such as sex and sites, will be explored. The intra-subject correlation will be estimated from the variances of the random intercepts and residuals. Other outcome variables, such as other biomarkers and questionnaire data, can be analyzed in a similar way. The estimates about the variability of data and intrasubject correlations will be useful for designing a subsequent larger study.

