9.4.4 SAFETY ANALYSES

The frequency and severity of AEs in the placebo and IN groups will be calculated and compared statistically. Because IN is a common medication that has been in use for many decades its adverse effect profile is already well known, and we do not expect data from this pilot study to materially change our understanding of its adverse effects.

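### No safety population is defined: the only sets in section 9.3 are completers and per-protocol, and if that default is applied to section 9.4.4 the between-arm adverse event comparison omits participants who stopped because of an event

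*Combined protocol and SAP*

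**What the plan says.** Section 9.3 is the only place that sets analysis populations. It gives two. The first is completers: "the entire study population completing the study protocol will be utilized for most analyses". The second is a per-protocol set, illustrated by an 80% intake on 80% of days: "Per-Protocol analysis will be used primarily". No safety, as-treated or intention-to-treat set is named.

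Section 9.4.4 then plans the adverse event comparison: "The frequency and severity of AEs in the placebo and IN groups will be calculated and compared statistically". It gives no population, denominator or test. By contrast, section 9.4.2 does name its own set for the primary PGE2 model, using data "from both baseline and day 28 from all randomized patients".

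Several rules move participants out of the completer set for reasons that can be adverse events:
- Section 7.2 lists as a ground for withdrawal: "Other acute illness that requires breaking study blinding and discontinuing study medication for clinical reasons".
- Section 7.2 also lists hospitalization for acute pancreatitis. Under section 5.2 such participants "will be withdrawn from the study, and considered non-accrued", and section 4.1 says much the same.
- Section 7.2 allows withdrawal for taking less than 66% of doses.

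Section 4.1 sets the scale: "Up to 40 participants will be enrolled in order to accrue 32 participants who complete the study protocol". It also provides for replacement of a withdrawn participant, "and the following subject will be assigned the same allocation"; the parallel text in section 6.3 omits that clause.

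**The concern.** Stopping treatment is often a consequence of an adverse event, so completion is an outcome of treatment and not a neutral way to choose who is counted for safety. An analyst who finds no set in section 9.4.4 will look to section 9.3, and both sets there are conditioned on having tolerated the drug. The participants most informative about harm would be missing from the numerator and the denominator.

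Some of the missing events could be serious. Section 8.3.2 makes inpatient hospitalization a criterion for seriousness, so a participant hospitalized for acute pancreatitis on study has an SAE and is also outside the completer set. Side effects can also act through adherence: section 4.3 calls dyspepsia and similar effects often dose related, and a participant who skips capsules for that reason can be withdrawn under section 7.2 or fall below the per-protocol example.

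The replacement clause in section 4.1 would hide the pattern. Because the next participant takes the same allocation, the arms refill toward 16 each, and the completer denominators can look balanced even when withdrawals were not.

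**Working it through.** The plan states no adverse event or discontinuation figure, so there is nothing to reproduce on this point. The power figures in section 9.2 concern PGE2 and do not enter.

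**Step 1. Which set applies to each analysis**

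| Analysis | Section | Set named |
|---|---|---|
| Primary PGE2 model | 9.4.2 | All randomized |
| Most analyses | 9.3 | Completers |
| Primary use | 9.3 | Per-protocol (defined by example) |
| Adverse events by arm | 9.4.4 | None |

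The only stated defaults available to section 9.4.4 are the two in section 9.3.

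**Step 2. Room for loss**

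From section 4.1: 40 - 32 = 8 non-completers, and 8/40 = 20% of those enrolled. This counts enrolled, not dosed, participants. Some of the 8 may never take drug: screen failures (5.4), abnormal creatinine (8.2), or ulceration at the baseline endoscopy (5.2). The per-protocol set could in turn exclude participants who did complete. The 20% is an indication of scale, not a bound in either direction.

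**Step 3. One arm, assumed counts**

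Assume 20 dosed on indomethacin, 4 not completing, 16 completing, and no event in any completer. Let s be the number who stop because of an event. The dosed analysis shows s/20 and the completer analysis shows 0/16 whatever s is. For 0/n the exact (Clopper-Pearson) upper limit is 1 - 0.025^(1/n); for n = 16 it is 0.206. Other limits come from the beta quantiles.

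| s | Dosed | Exact 95% CI | Completers | Exact 95% CI |
|---|---|---|---|---|
| 0 | 0/20 = 0% | 0-17% | 0/16 | 0-21% |
| 1 | 1/20 = 5% | 0.1-25% | 0/16 | 0-21% |
| 2 | 2/20 = 10% | 1-32% | 0/16 | 0-21% |
| 4 | 4/20 = 20% | 6-44% | 0/16 | 0-21% |

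The understatement runs from nil at s = 0 to 20 percentage points at s = 4.

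**Step 4. Both arms, assumed counts**

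Assume 20 dosed per arm, 8 non-completers in total, and 2 completers with an event in each arm. Let x indomethacin participants stop for an event; the other 8 - x non-completers are on placebo without an event. The dosed comparison is (2 + x)/20 against 2/20. The completer comparison is 2/(20 - x) against 2/(12 + x). P values are two-sided Fisher exact.

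| x | All dosed, IN vs placebo | p | Completers, IN vs placebo | p |
|---|---|---|---|---|
| 0 | 2/20 vs 2/20 (10% vs 10%) | 1.00 | 2/20 vs 2/12 (10% vs 17%) | 0.62 |
| 4 | 6/20 vs 2/20 (30% vs 10%) | 0.24 | 2/16 vs 2/16 (12.5% vs 12.5%) | 1.00 |
| 6 | 8/20 vs 2/20 (40% vs 10%) | 0.065 | 2/14 vs 2/18 (14% vs 11%) | 1.00 |
| 7 | 9/20 vs 2/20 (45% vs 10%) | 0.031 | 2/13 vs 2/19 (15% vs 11%) | 1.00 |
| 8 | 10/20 vs 2/20 (50% vs 10%) | 0.014 | 2/12 vs 2/20 (17% vs 10%) | 0.62 |

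At x = 4 a 20-point difference among dosed participants disappears among completers. At x = 0 the dosed rates are equal, but the completer rates differ only because event-free placebo non-completers have left the denominator.

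**The case against.** The strongest reply is that nothing in the plan puts safety on completers. Section 9.3 speaks of most analyses, which leaves room for exceptions, and section 9.4.2 already departs from it. Section 9.4.4 refers to the two groups with no completer limit. Counting a participant as non-accrued may mean only that the accrual target is not credited. All of this stands. A reader might infer that the analysis rule itself discards these participants; the text supports only the weaker statement that the safety population is undefined and the stated defaults would leave them out.

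It also stands that the events are not lost. Section 8.3.4 records every on-study event, section 10.1.6 sends all of them to the DSMB, section 8.3.7 promises a published summary with no completer limit, and the halting rules in 7.1 and 10.1.6 do not depend on section 9.3. But none of these sections sets a denominator for the comparison in 9.4.4.

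A reader might further infer that a later, longer trial would rest on this adverse event table. The documents do not say so: section 9.4.4 does not expect this pilot to change what is known about the drug's adverse effects, section 4.1 ties the next study to the PGE2 result, and safety is not among the objectives or endpoints in section 3.

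Finally, the examples are assumed, and the s = 4 case is extreme because every event falls in a participant who stopped. Even 4/20 against 0/20 gives a two-sided Fisher p of about 0.11, and in step 4 the dosed comparison passes 0.05 only at 7 or 8 stops. That is fair: with arms this small the issue is a misleading rate more than a missed significant result. Nor is the direction of bias in the difference certain. Omitting withdrawn participants with events lowers the rate in whichever arm they belong to, and pancreatitis withdrawals can occur on placebo.

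**Conclusion.** The point holds as a gap with a predictable consequence. Section 9.4.4 commits to a between-arm comparison with no stated population, and the only defaults in the plan are conditioned on completion or adherence. Applying either would understate adverse event rates when participants stop because of events. It would understate the indomethacin-placebo difference only if drug-related events cause more stopping on indomethacin than on placebo.

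The size cannot be derived from the documents, since they give no rate of stopping for adverse events. The illustrations rest on assumed counts, including 20 dosed per arm, which the plan does not state. Recording, DSMB oversight, halting rules, sample size and the primary endpoint are untouched. This should be fixed, but it is not a defect that would by itself invalidate the trial.

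**What to change.** Add to section 9.3, and cite in section 9.4.4: safety analyses include every randomized participant who took at least one dose of study drug, grouped by treatment received, including those withdrawn, replaced or counted as non-accrued. Report endoscopy- and secretin-related events for everyone who had a study endoscopy, since these can occur before any dose. Give counts and exact 95% intervals by arm.

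The population should be fixed before unblinding. Because sections 9.3 and 9.4.4 are protocol text, the cost is a short amendment with IRB approval. The adverse event data are already collected under section 8.3.4, so no new data, visits or participants are needed.

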9.4 STATISTICAL ANALYSES

9.4.1 GENERAL APPROACH

For descriptive statistics, categorical and continuous data will be presented as percentages or medians with ranges as appropriate. P-values < 0.5 will be considered statistically significant.

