9 STATISTICAL CONSIDERATIONS

9.1 STATISTICAL HYPOTHESES

Primary Endpoint:

- Decrease in mean pancreatic juice PGE₂ concentration after indomethacin treatment, to no more than 66% of baseline, and statistically significant in comparison to placebo.

Secondary Efficacy Endpoints:

- Changes in salivary and blood PGE₂ concentrations after study drug administration will have statistically significant correlation with changes in PJ PGE₂ concentrations and blood IN levels.
- Salivary and blood PGE₂ concentrations will have statistically significant correlation with PJ PGE₂ concentrations.
- Improvement in pain and quality of life of study participants will have statistically significant correlation with post-treatment changes in PJ PGE₂ concentrations.
- Exploratory analysis of molecular analytes (cytokine and microbiome) in blood and saliva will be done to measure effect of IN administration.

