9.2 SAMPLE SIZE DETERMINATION

We plan a sample size of 16 patients per treatment arm. Since this is a pilot study, this sample size is largely limited by budgetary restraint and is too small for a sequential study design. However, this sample size is adequate for studying the primary hypothesis with a two-sample two-sided t-test on the mean PGE₂ level at day 28 between the randomized groups. We expect to show that the treatment group has significantly lower mean PGE₂ than the placebo group. In our previous publication on PJ PGE₂,²⁰ we reported that median PJ PGE₂ level in 10 CP patients was 307 pg/ml with IQR of 249-362 pg/ml and standard deviation of 84 pg/ml. The boxplot of that data suggests that normality is a reasonable distributional assumption for the PGE₂ data. That study also found that mean PJ PGE₂ in a healthy control group was 104 pg/ml, about one third of the mean level of the CP group. If we conservatively assume that the control group in the proposed trial has 50% decrease in mean, with a Type I error of 0.05, the power of the t-test is 0.998. If we use an even more conservative mean for the control group, with 1/3 reduction in mean PGE₂, the power is 0.94. If we additionally assume that there is some data loss (due to consent withdrawal, dropout, or specimen mishandling) so that the sample size per treatment group is 12 instead of 16, the statistical power decreases to 0.85, but is still reasonable. Note that the large statistical power in the calculation above is a result of the relatively small standard deviation of the PGE₂ compared with our working assumption on the mean reduction. This assumption is supported by the data in Abu Dayyeh et al.²⁰ If this pilot study is successful, we will conduct a future study that focuses on patient centered outcomes; that study is expected to have a larger sample size because those outcomes are expected to be less sensitive to the treatment than biomarkers. The data from this pilot study will provide critical preliminary and feasibility data for the future investigation.

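### Section 9.4.1 sets the significance threshold at p < 0.5, ten times the 0.05 used to size the trial, so half of all true-null comparisons would be called significant

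*Combined protocol and SAP*

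**What the plan says.** Section 9.4.1 (General Approach) states: "P-values < 0.5 will be considered statistically significant". No other sentence in the document sets a general cut-off for the analyses.

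Section 9.2 (Sample Size Determination) works from a different figure. The test is a "two-sample two-sided t-test on the mean PGE₂ level at day 28 between the randomized groups", and the first power statement reads "with a Type I error of 0.05, the power of the t-test is 0.998". The sample size text in section 4.1 gives the same Type I error.

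Several parts of the plan depend on what counts as significant:

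- The primary endpoint (synopsis, section 3 and section 9.1) requires a fall in mean pancreatic juice PGE₂ "to no more than 66% of baseline, and statistically significant in comparison to placebo".
- Section 4.1 makes longer-term trials at this dose conditional on a statistically significant decrease of at least one third.
- Three of the secondary hypotheses in section 9.1 are framed as correlations that will reach statistical significance.
- Section 9.4.4 says that adverse events will be compared statistically between arms.

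**The concern.** The threshold used to judge the results is ten times the one used to design the trial. An analyst who follows section 9.4.1 would call a comparison significant at p = 0.4. An analyst who follows section 9.2 would not.

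The primary endpoint has two parts, and the threshold governs the second, the comparison with placebo. According to section 4.2, the placebo arm is there to control for changes in PGE₂ over time from other causes. At p < 0.5 that control is weak.

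The secondary correlation hypotheses have no numerical criterion alongside significance, so the threshold alone decides them. They are meant to show whether saliva or blood can stand in for pancreatic juice and whether pain and quality of life track PGE₂. A false positive on either would carry into the design of the next trial.

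**Working it through.** **Inputs.** All are from section 9.2.

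- Sample size: "We plan a sample size of 16 patients per treatment arm".
- Reference level and spread: "307 pg/ml with IQR of 249-362 pg/ml and standard deviation of 84 pg/ml". The 307 is a median; I use it as the mean, as the plan appears to do.
- Effects: a reduction of one half (0.5 × 307 = 153.5 pg/ml) or of one third (307 / 3 = 102.3 pg/ml). The text attributes the decrease to the control group. Only the difference between arms enters the formula, so this does not affect the arithmetic.
- Test: two-sided, two-sample, alpha 0.05.

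**Step 1: reproduce the stated power.** By the normal approximation, power = Φ(δ / SE − z), with SE = 84 × √(2/n).

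- n = 16: SE = 84 × √(2/16) = 29.7 pg/ml.
- n = 12: SE = 84 × √(2/12) = 34.3 pg/ml.

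The value of z is 1.960 at two-sided 0.05 and 0.674 at two-sided 0.5.

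| Scenario | δ / SE | Stated power | Power at 0.05 | Power at 0.5 |
|---|---|---|---|---|
| 50% reduction, 16 per arm | 153.5 / 29.7 = 5.17 | 0.998 | 0.999 | 1.000 |
| 1/3 reduction, 16 per arm | 102.3 / 29.7 = 3.45 | 0.94 | 0.931 | 0.997 |
| 1/3 reduction, 12 per arm | 102.3 / 34.3 = 2.98 | 0.85 | 0.847 | 0.990 |

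The stated figures agree with 0.05 to within about 0.01. The stated 0.94 and 0.85 cannot come from 0.5. With a reference mean of 312 (3 × 104, from the healthy-control comparison), the values at 0.05 are 0.9995, 0.939 and 0.858, which leads to the same conclusion. An exact noncentral t calculation at 0.05 gives 0.999, 0.915 and 0.814. The plan's figures therefore look like normal approximations, but this does not affect which threshold was intended.

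**Step 2: error rate at the written threshold.** A valid two-sided test at p < 0.5 rejects a true null with probability 0.50, against 0.05: a factor of 10. For three independent true-null tests (an illustrative number), the chance of at least one false positive is 1 − 0.5³ = 0.875, against 1 − 0.95³ = 0.143.

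**Step 3: smallest significant difference.** Using the day 28 t-test with 30 degrees of freedom:

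- At 0.05: critical |t| = 2.042, and 2.042 × 29.7 = 60.7 pg/ml, or 19.8% of 307.
- At 0.5: critical |t| = 0.683, and 0.683 × 29.7 = 20.3 pg/ml, or 6.6% of 307.

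**Step 4: smallest significant correlation.** With n = 32, r = t / √(t² + 30):

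- At 0.05: 2.042 / √(4.17 + 30) = 0.349.
- At 0.5: 0.683 / √(0.466 + 30) = 0.124.

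**The case against.** The strongest reply is that this is a plain typing error, that sections 4.1 and 9.2 both give 0.05, and that no analyst would apply 0.5. That is very probably right about the cause. It does not remove the problem: the wrong figure stands in the one sentence that defines significance for the analyses, and section 9.2 states its alpha only for the power calculation on the primary comparison. If the text stays as it is, the analyst must either use a 50% error rate or depart from the written plan after the data are in.

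Three further points limit the consequences.

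- **Direction.** The primary claim is a decrease, so at two-sided 0.5 a false claim in favour of indomethacin has probability 25%, not 50%. This is correct, and the ratio to plan is still tenfold (25% against 2.5%).
- **The 66% criterion.** If PGE₂ does not change in the indomethacin arm, its mean would have to fall by 0.34 × 307 = 104 pg/ml by chance. Assuming a within-subject correlation of 0 (the plan gives none), the SE of the mean change is 84 × √2 / √16 = 29.7 pg/ml, and the probability is about 0.0002. It is smaller still at higher correlation. So under no change the go decision is well protected. It is not protected if both arms fall together, which is the case the placebo arm exists to detect, and the criterion does not support a stand-alone claim of significance against placebo.
- **The illustrative cut-offs.** The primary analysis in section 9.4.2 is a random intercept model, possibly on transformed data, and not the day 28 t-test. For a contrast in change from baseline, the cut-offs at 0.5 and 0.05 would be about 29 and 86 pg/ml at a within-subject correlation of 0, 20 and 61 at 0.5, and 13 and 38 at 0.8. For correlations with blood indomethacin, only about 16 treated participants are informative, and the critical |r| is about 0.18 and 0.50. The cut-offs move, but the error rates do not.

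It is also true that section 4.1 labels the correlation hypotheses exploratory, and section 9.4.9 does the same for pain and quality of life. That lowers the stakes, but section 9.1 still frames the hypotheses in terms of significance, and nowhere does the plan argue for a relaxed alpha because this is a pilot.

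**Conclusion.** The concern holds. Section 9.4.1 contradicts section 9.2, and the plan's own power figures identify 0.05 as the intended level. As written, the two-sided false-positive rate for each true-null comparison is 0.50 instead of 0.05, for any valid test. The cut-offs of about 20 against 61 pg/ml rest on the day 28 t-test with 16 per arm and an SD of 84 pg/ml; those of 0.12 against 0.35 rest on 32 participants contributing to a correlation. The primary go decision is partly protected by the 66% criterion. The placebo comparison taken alone and the secondary correlations are not. A probable typing error in the rule that decides success still has to be corrected before the data are analysed.

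**What to change.** In section 9.4.1, replace the 0.5 threshold with a two-sided threshold of p < 0.05, matching the sidedness and Type I error in section 9.2. Make the correction before unblinding. It changes one line and needs no change to sample size, procedures, visits or data collection.
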